5.4.1 Discontinuation from Study Treatment

Subjects who discontinue study treatment will still continue study follow-up procedures. Investigators are encouraged to assess all subjects according to the study protocol even after discontinuation from study treatment.

- Investigators can discontinue subjects from study treatment in case of unacceptable toxicity, non-compliance, disease progression requiring alternative therapy, or if the investigator determines it is in the subject's best interest.
- Astex Pharmaceuticals may require that a subject is discontinued from treatment for safety reasons or for noncompliance.

In all cases, the reason(s) for discontinuation from study treatment must be recorded in the source document and on the relevant page of the subject's case report form or electronic case report form (CRF/eCRF).

It is important to obtain protocol-specified follow-up information on any subject discontinued from study treatment. Section 10.0 describes follow-up for AEs. Subjects should be followed for survival information until death, withdrawal of consent, or termination of the clinical trial. Safety should be followed for 30 days after the last dose of study treatment, or until the subject starts alternative anti-leukemia treatment for AML (except for hydroxyurea as specified in Section 7.4.1), whichever happens earlier (see Section 10.4). Collection of AEs and concomitant medications may also continue until the decision is made to permanently discontinue study treatment. Subjects in the BSC group will be considered to be on study treatment until they have disease progression.

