7.4 Concomitant Treatment

On the concomitant medication CRF/eCRF, document all medications a subject takes, starting from 14 days before randomization and ending 30 days after the last dose of study treatment, or start of new anti-leukemia treatment for AML (except for hydroxyurea as specified in Section 7.4.1), whichever is first. Collection of concomitant medications may also continue until the decision is made to permanently discontinue study treatment (in the event that this decision occurs more than 30 days after the last dose of study treatment). Prior anti-AML and anti-MDS therapy should be documented regardless of timing with randomization. Include supportive or palliative treatment whether prescription or nonprescription. Include start and stop dates and indication.

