8.2 Myelosuppression (Neutropenia, Febrile Neutropenia, Thrombocytopenia, and Anemia)

Myelosuppression is the primary toxicity associated with administration of guadecitabine and its effects after 5 consecutive days of administration are maximal between Days 15 and 22 in a cycle with recovery in 1 to 3 weeks. With the 10-day regimen (dosing on Days 1-5 and 8-12 or on Days 1-10) the nadir is lower and lasts longer than with the 5-day regimen. Pancytopenia is a hallmark of AML and MDS and may aggravate or obscure the effects of guadecitabine. However, if a clinical response occurs and normal hematopoietic cells repopulate the bone marrow, neutropenia and thrombocytopenia may abate.

Complete blood and platelet counts should be performed as needed to monitor counts. Since myelosuppression and infection events are also manifestations of the underlying disease of AML, careful investigator judgment regarding relationship to treatment is important to guide the decision whether to dose delay, dose reduce, or both. The cyclic nature of myelosuppression (reduction of counts between Day 8-15 and trend to recover by Day 22-28 or later) could be more indicative of a drug effect, while persistent low counts regardless of treatment is probably more indicative of a disease effect that needs to be treated without dose delay. Investigators should use their clinical judgment guided by the recommendations for dose adjustment for guadecitabine described above (see Section 7.3.1), and should use the guidelines of dose adjustment for TC options as per their local prescribing information and standard practice.

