10.2 Adverse Event Reporting and Descriptions

Record new AEs from the start of study treatment until 30 days after the last dose of study treatment or until the subject starts new anti-AML treatment, including new investigational treatment, whichever occurs first. Collection of AEs may also continue until the decision is made to permanently discontinue study treatment. Related SAEs should be collected until the end of the study or the subject's death. Record screening procedure-related AEs that occur before the start of study treatment.

Record all AEs either observed by the investigator or one of his or her medical collaborators, or reported by the subject spontaneously, or in response to the direct question below, in the AEs section of the subject's CRF/eCRF, in the source document, and if applicable, record on the SAE form. Whenever possible, the investigator should group signs and symptoms (including laboratory tests or other results of diagnostic procedures) into a single diagnosis under a single term. For example, cough, rhinitis, and sneezing might be reported as "upper respiratory infection" or a pulmonary infiltrate, positive sputum culture and fever might be reported as "pneumonia."

To optimize consistency of AE reporting across centers, ask the subject a standard, general, nonleading question to elicit any AEs (such as "Have you had any new symptoms, injuries, illnesses since your last visit?").

Death is an outcome of an SAE and usually not itself an SAE, unless it is death with no identifiable cause or event. In all other cases, record the cause of death as the SAE. Investigators will assess the status of previously reported, and occurrence of new AEs and SAEs at all subject evaluation time points during the study.

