7.4 Safety Variables and Analyses

Unless otherwise specified, all safety analyses will be performed using the Safety Analysis Set which includes data from all subjects who receive any amount of study treatment (guadecitabine or TC; see Section 5.2). For all safety analyses, summaries by treatment group (guadecitabine and TC) will be provided. Additional displays of study treatment exposure and adverse events may be generated for each preselected TC option. Data will be summarized by guadecitabine and each TC option within a given preselected TC option.

Safety is assessed by subject-reported and investigator-observed AEs, and 30-day and 60 day allcause mortality, along with concomitant medications, physical examination, clinical laboratory tests (hematology, serum chemistry, and urinalysis), vital signs, ECOG performance status, and ECGs. Safety is also assessed by exposure to guadecitabine or TC, reasons for discontinuation, deaths and causes of deaths.

All safety data collected during the study will be included in the study database. All safety data collected during the study will be used for generation of safety summary tables, with the exception of AEs and medications. The AE and medication summary tables will only include treatment-emergent AEs and concomitant medications as defined in Sections 7.4.2 and 7.4.4.

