7.4.2 Adverse Events

AE terms reported by study subjects or observed by investigators will be mapped to the appropriate System Organ Class (SOC) and Preferred Term (PT) according to the Medical Dictionary for Regulatory Activities (MedDRA). Severity of AE will be graded using Common Terminology Criteria for Adverse Events (CTCAE) version 4.03.

Treatment-emergent AEs are defined as events that first occurred or worsened after the first dose of study drug given on C1D1 (or the C1D1 visit date for subjects randomized to BSC) until 30 days after the last dose of study treatment (or until the Safety Follow-up visit date for subjects randomized to BSC), or the start of an alternative anti-leukemia treatment, whichever occurs first, with the following exceptions: events that occurred after 30 days beyond the last dose of study treatment (or after the Safety Follow-up visit date for subjects randomized to BSC), or the start of an alternative anti-leukemia treatment, whichever occurs first, with the following exceptions: events that occurred after 30 days beyond the last dose of study treatment (or after the Safety Follow-up visit date for subjects randomized to BSC), or the start of an alternative anti-leukemia treatment will also be considered treatment-emergent if the events are both serious and related to the study treatment. For the purpose of determining whether an AE is a treatment-emergent AE, incomplete AE start dates will be imputed conservatively.

All AE data collected in the study database will be listed, including those that are not treatment emergent. However, safety tables will be generated based only on treatment-emergent AEs.

An overall safety summary table containing counts and percentages of subjects with any AE, any AE Grade \geq 3, AE resulting in permanent treatment discontinuation, AE resulting in drug interruption, AE resulting in dose reduction, any serious AE (SAE), and subcategories of SAEs (fatal and non-fatal) will be produced by treatment group. A similar table with related AE counts will also be produced by treatment group. Related events are those that the investigator considered to be suspected to be related to study treatment as described in the study protocol.

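### For dosed subjects the adverse-event tables close 30 days after the last dose, even in a treatment hold with no decision to stop, so some late events count only if dosing resumes

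*Protocol*

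**What the plan says.** **Collection.** Protocol 10.2 sets the required period: "Record new AEs from the start of study treatment until 30 days after the last dose of study treatment", or to new anti-AML treatment if that is earlier. For the time beyond it, 10.2 says "Collection of AEs may also continue until the decision is made to permanently discontinue study treatment", and 5.4.1 has the same permissive sentence: "Collection of AEs and concomitant medications may also continue until the decision is made to permanently discontinue study treatment". Protocol 7.4, on concomitant medications, names the situation: "in the event that this decision occurs more than 30 days after the last dose of study treatment". Related serious events are treated differently: "Related SAEs should be collected until the end of the study or the subject's death".

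**The late visit.** Under Protocol 9.5.5, if the decision to stop comes 30 (+7) days or more after the last dose, the Safety Follow-up visit is held on the decision day or as soon as possible afterwards. All AEs are collected there.

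**Analysis.** SAP 7.4.2 closes the treatment-emergent window at 30 days after the last dose, or at alternative anti-leukemia therapy if earlier. For BSC the end is the Safety Follow-up visit date. Later events "will also be considered treatment-emergent if the events are both serious and related to the study treatment". SAP 7.4 adds that "The AE and medication summary tables will only include treatment-emergent AEs". SAP 7.4.4 uses the same end points for medications, with an exception for those treating a related serious event.

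**The concern.** Holds for count recovery are part of the design. Protocol 7.1.2 delays Cycle 2 when marrow blasts are below 5% and counts are low. Table 5 provides for recovery after a delay of more than a week. Table 7 (footnote d) limits logistical delays to 7 days, but no maximum is given for count-recovery delays. A subject can therefore be more than 30 days past the last dose with no decision to stop, and the protocol foresees this.

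The analysis window ignores it. Whether an AE late in a hold is tabulated depends on what happens next. If the subject is re-dosed, the last dose moves forward and the event counts. If the subject stops or dies, it counts only when it is both serious and judged related. The subjects affected are those whose counts did not recover.

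The relatedness test is a weak safeguard here. Protocol 8.2 says that myelosuppression and infection are also manifestations of AML, and investigators are not blinded (6.2). The end rule also differs between BSC and every dosed regimen, which matters because SAP 7.4 allows AE displays by preselected treatment choice.

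**Working it through.** The plan states no figure for this point, so there is nothing to reproduce. The check is day arithmetic from the stated schedules.

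**1. Day on which the window closes.** Inputs are the last dosing days in Protocol 7.1.2 and 7.2. Closing day = last dosing day + 30.

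| Final-cycle regimen | Last dosing day | Window closes |
|---|---|---|
| Guadecitabine Days 1-5; decitabine; MEC | 5 | Day 35 |
| HiDAC (up to 6 days) | 6 | Day 36 |
| Azacitidine | 7 | Day 37 |
| Guadecitabine Days 1-10; LDAC | 10 | Day 40 |
| Guadecitabine Days 1-5 and 8-12 | 12 | Day 42 |

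FLAG is omitted. Its G-CSF runs from Day 6 to white cell recovery, and the plan does not say whether G-CSF counts as the last dose.

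**2. Comparison with expected recovery.** Protocol 8.2 describes myelosuppression after 5 days of dosing as "maximal between Days 15 and 22 in a cycle with recovery in 1 to 3 weeks". Counting recovery from the nadir, the range is Day 15 + 7 = Day 22 to Day 22 + 21 = Day 43. The late end lies 43 - 35 = 8 days beyond the close. The nadir itself is inside every window. For the 10-day regimen, 8.2 gives no recovery days; it says only that the nadir is lower and lasts longer.

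**3. Uncovered days.** Assume a hold that ends in permanent discontinuation w weeks after Day 29. Uncovered days = max(0, 29 + 7w - closing day).

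| Hold past Day 29 | 5-day (closes 35) | Days 1-10 (closes 40) | Days 1-5 and 8-12 (closes 42) |
|---|---|---|---|
| 1 week | 1 | 0 | 0 |
| 2 weeks | 8 | 3 | 1 |
| 3 weeks | 15 | 10 | 8 |
| 4 weeks | 22 | 17 | 15 |

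**4. One event under each rule.** Take a pneumonia with onset on Day 38 of a hold after a 5-day cycle, judged unrelated.
- Dosing resumes on Day 43: the last dose is now Day 43 or later, so Day 38 is inside the window and the event is tabulated.
- Treatment is stopped on Day 43: 38 is greater than 35, so the event is not tabulated, even though the visit required by 9.5.5 would collect it.
- A BSC subject with the same event before the Safety Follow-up visit and before any alternative therapy: the event is tabulated.

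**5. Number of subjects.** This cannot be derived. As illustration only, let q be the share of treated subjects ending in such a hold, L the uncovered days and h the daily hazard of Grade 3 or higher infection, all assumed. Share with an event = q x (1 - exp(-h x L)).
- Low: 0.10 x (1 - exp(-0.005 x 7)) = 0.3%, or 0.5 of 150 subjects.
- High: 0.30 x (1 - exp(-0.015 x 14)) = 5.7%, or 8.5 of 150.
- High values with L held to the 8 days of step 2: 0.30 x (1 - exp(-0.12)) = 3.4%, or 5.1 of 150.

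These are gross counts. They do not remove serious, related events, which the SAP keeps, or subjects already counted for an earlier event.

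**The case against.** A reader might infer that toxicity of a final cycle without count recovery disappears from the safety tables. The documents do not support that:
- Events starting or worsening by last dose + 30 days are counted, including those at the nadir.
- Serious, related events stay treatment-emergent afterwards, and the protocol requires their collection.
- SAP 7.4.5 tabulates laboratory shifts to the worst grade during the study and new or worsening Grade 3 or higher abnormalities, so prolonged cytopenia remains visible.
- SAP 7.4.3 summarises all deaths by cause for all randomized subjects, and all collected AEs are listed.

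A reader might also infer that sites are free to collect nothing during a hold. That goes too far. Protocol 10.2 also has investigators assess new AEs at all evaluation time points, 7.1.2 requires at least weekly blood counts during a Cycle 2 delay, and 9.5.5 requires the late visit. The permissive sentences conflict with these requirements but do not override them.

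There is also a fair case for last dose + 30 days. It is one fixed rule for every dosed regimen, whereas a window that ends on an investigator's decision lets an unblinded choice set its length. This is a good reason to keep the fixed-window tables and add the extended ones beside them. It does not remove the dependence on whether dosing later resumes, or the different rule for BSC.

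**Conclusion.** The point holds in a narrow form. For dosed subjects whose hold runs past last dose + 30 days and ends in discontinuation or death, AEs that start or worsen in the interval before the decision are left out of the AE tables if they are non-serious, or serious but judged unrelated. The same events count if dosing resumes. Collection in that interval is worded as permissive in 5.4.1 and 10.2, while 9.5.5 requires AEs to be collected at the decision-day visit.

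The size is known in days only: up to 8 days between the Day 35 close and the latest recovery day implied by 8.2 for the 5-day regimen, counting recovery from the nadir, and more if a hold lasts longer. The range in subjects rests wholly on assumed inputs and should not be cited as an estimate. The primary survival analysis is unaffected. The point concerns completeness and comparability of the AE summaries and is worth settling before the final database lock, which SAP 6.0 describes as still to come.

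**What to change.** **SAP 7.4.2, and 7.4.4 for medications.** Add summaries, for all arms, with the window ending at the later of (a) last dose + 30 days and (b) the Safety Follow-up visit or treatment-discontinuation date. For BSC, which has no last dose, (b) alone applies. Keep the cut at alternative anti-leukemia therapy and the exception for serious, related events. State which date in (b) takes precedence, and what applies when a subject dies before the visit. Show these beside the last dose + 30 days tables.

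The dates should be obtainable. The SAP already uses the Safety Follow-up visit date for BSC, and its event-free survival definition needs a treatment-discontinuation date. The documents do not show that a separate decision date is recorded on the case report form, so the fix should not depend on one.

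**Protocol 5.4.1, 7.4 and 10.2.** For subjects still on treatment, reconcile the permissive collection wording with the collection required in 9.5.5. This will change little, since enrollment closed in September 2018.

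**Cost.** One further set of tables. A few more disease-related events will count as treatment-emergent. Because the routine visit falls at 30 (+7) days, some subjects without a long hold gain up to 7 days of window. Recording during past holds may be incomplete, and a footnote to the tables should say so.

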5.4.2 Withdrawal from the Study

Subjects may withdraw consent for the study at any time, or subjects may be lost to follow-up. The term *withdrawal of consent* should not be used simply because the subject no longer wishes to receive randomized treatment or actively continue to return for follow-up assessments or simply to justify why efforts are not being made to continue to follow some subjects who have discontinued their randomized intervention or wish to participate in another study after discontinuing study treatment. Rather, the term should be used only when the subject no longer wishes to participate in the trial and no longer authorizes the investigators to make efforts to continue to obtain their outcome data. Ideally, if subjects withdraw their consent, it should be done in writing. Investigators will be educated and evaluated about the proper use of the term *withdrawal of consent*, and the DMC will regularly assess whether the term is being used properly.

It is important to obtain follow-up information, according to standard medical practice, on any subject withdrawn prematurely from the study. Every effort must be made to undertake at least standard assessments that are critical for efficacy or safety evaluation, such as disease progression (if the subject did not withdraw because of disease progression), subsequent anti-leukemia treatment, survival information, and safety data.

The investigator must also ensure the subject understands that his or her medical records may continue to be available for the follow-up period as described in the approved informed consent form (ICF).

5.4.3 Replacement of Subjects

Subjects will not be replaced in this study. Astex Pharmaceuticals may stop the study at any time. In this event, Astex will make reasonable efforts to ensure subjects are transitioned off the study in an orderly manner.

6.0 ENROLLMENT, RANDOMIZATION, AND BLINDING PROCEDURES

Subjects will be screened at each study center for assessment of eligibility for the study. Each subject will be assigned a unique number (subject number) which will comprise the center number and the assigned subject number within the center. This number will be used to identify the subject throughout the study.

6.1 Randomization

Eligible subjects will be randomly assigned to study treatment. Treatment assignments for the individual subjects will be determined through a computer generated randomization scheme and accessed through an interactive response system. Instructions for access and use of the interactive response system for randomization will be provided to participating study centers separately.

Randomization will be 1:1 between guadecitabine and TC groups, and will be stratified by intensity of preselected TC option (high intensity vs low intensity vs BSC), ECOG performance status (0-1 vs 2), baseline cytogenetics (poor risk vs other; see Appendix 3), and study center region (North America vs ROW).

Selection of 1 of the TCs must be made prior to the randomization of each subject. Subjects should receive study treatment as soon as possible after randomization (maximum of 1 week between randomization and treatment).

6.2 Blinding

The sponsor, investigators, and study subjects are not blinded in this study. However, to minimize the potential bias associated with assessment of treatment outcome, evaluation for response may be performed by a blinded independent central reviewer. The specific process used for handling test samples and reports will be described separately.

7.0 STUDY TREATMENTS

Guadecitabine is the Investigational Medicinal Product (IMP) (Section 7.1), and the active comparator consists of the TC options (Section 7.2).

7.1 Investigational Medicinal Product: Guadecitabine

Guadecitabine (2'-deoxy-5-azacytidylyl- $(3'\rightarrow 5')$ -2'-deoxyguanosine sodium salt) is a dinucleotide incorporating decitabine with deoxyguanosine via a 3' \rightarrow 5' phosphodiester bond.

7.1.1 IMP Information

Guadecitabine (formerly known as SGI-110)	
SGI-110 for Injection, 100 mg,	
SGI-110 Diluent for Reconstitution	

The sponsor recommends following Occupational Safety and Health Administration (OSHA) Guidelines for handling cytotoxic drugs outlined in Yodaiken and Bennett (1986) or similar institutional or country-specific guidelines. Preparation should occur according to institutional practice. For skin contact or spillage, refer to the material safety data sheet (MSDS) for treatment options.

Reconstituted drug product is intended for SC administration at a recommended concentration of 100 mg/mL.

Records of the receipt and dispensing of drug supplies will be kept at the study centers and reconciled at the end of the study to provide a complete accounting of all used and unused IMP.

7.1.2 IMP Regimens and Administration

Guadecitabine will be given SC at a dose of 60 mg/m^2 in 28-day cycles (delayed as necessary to allow blood count recovery, see Section 7.3.1). For the first cycle guadecitabine will be given for

10 days on Days 1-5 and Days 8-12, or in the case of apparent progression during the first 5 days, guadecitabine can be given on Days 1-10 without interruption.

The second cycle will be 60 mg/m^2 for either 10 days (Days 1-5 and 8-12, or in the case of apparent progression, can be Days 1-10) or 5 days (Days 1-5 only) based on assessment of disease response, and hematological recovery at the end of Cycle 1, using the following general guidelines:

- Evidence of active leukemia in PB: no need for BM assessment, give second cycle with 10-day regimen with no delay.
- No evidence of active leukemia in PB: perform BM assessment and decide on course of action as follows:
 - BM blasts \geq 5%: give second cycle with the 10-day regimen with no delay.
 - BM blasts <5%: assess recovery of PB normal counts as follows:
 - Absolute Neutrophil Count (ANC) >500/µL *and* platelets >50,000/µL: give second cycle with no delay using the 5-day regimen.
 - ANC <500/µL *or* platelets <50,000/µL: Delay treatment and repeat PB at least weekly and give second cycle either as a 5-day regimen (if both counts recover to a higher level than the limit above with no PB blasts); or 10-day regimen (appearance of evidence of active leukemia with PB blasts regardless of normal count recovery).

For Cycles \geq 3, guadecitabine will be given for 5 days only (60 mg/m²/day, Days 1-5). These guidelines may be modified if it is believed to be in the best interest of the subject according to the treating physician's best clinical judgment. Treatment should be given for at least 6 total cycles in the absence of unacceptable toxicity or disease progression requiring alternative therapy. Beyond 6 cycles, treatment should continue as long as the subject continues to benefit based on investigator judgment. Guadecitabine treatment benefit may not manifest until at least 2 to 3 cycles and full response may need 6 or more cycles (Kropf et al 2015). Maintaining treatment after response is essential to avoid quick relapse (Cabrero et al 2015).

Administer guadecitabine by SC injection, preferably in the abdominal area, upper thigh, or arm. The total amount (in mg) of guadecitabine to be administered is determined by body surface area (BSA). In calculating BSA, use actual heights and weights. Do not adjust to "ideal" body weight. The institutional standard for calculating BSA is acceptable.

Take care to avoid intradermal injection, as this may result in injection site pain (see Section 8.4).

Additional guidelines regarding SC injection will be detailed in the Study Procedures Manual.

Investigators are prohibited from supplying guadecitabine to any subject not enrolled in this study or to any physicians or scientists except those designated as sub-investigators. The investigator must ensure that subjects receive guadecitabine only from personnel who fully understand the procedures for administering the study treatment.

